9. BIOMARKER, CORRELATIVE, AND SPECIAL STUDIES

9.1 Biomarker Studies

9.1.1 PK Analysis

Little is known about the potential for drug-drug interactions (DDI) of the triple combination of dabrafenib, trametinib, and AT13387. For this reason, extensive PK analysis will be performed during this study.

9.1.2 Tissue analysis of HSP90 inhibition

Subjects enrolled into the trial that have tumor tissue which is accessible for biopsy via FNA, core, or excisional will have tumor biopsies at the timepoints described in the study calendar. Specimens (approximately 50-100 mg/wet weight) will be analyzed in the lab of [name] at the Moffitt Cancer Center, [name]. Biopsy specimens and blood specimens will be evaluated via a novel mass spectrometry based assay to validate the role of increased HSP70 expression as a pharmacodynamic marker of HSP90 inhibition. Correlative studies will address whether HSP90 inhibition blocks the signaling pathways implicated in therapeutic escape including receptor tyrosine kinases, components of the mitogen activated protein kinase (MAPK) and PI3K/AKT signaling pathways.

Correlative studies will be performed to assess how changes in the expression of the key signaling proteins relate to patient response. The HSP client proteins and compensatory signaling molecules to be studied in the proteomic assay include Pathways and processes involved in the cell cycle (CDK1, CDK2, CDK4, cyclin D1, CHK1), receptor tyrosine kinases (ERBB2, IGF1R,), RAS/MAPK signaling (NRAS, HRAS, KRAS, SOS1, SHC1, BRAF, ARAF, CRAF, MEK1/2, c-Myc), PI3K/AKT signaling (AKT1, AKT2, AKT3, mTOR, CSK, FAK1, GSK3 β), B-catenin/WNT signaling (APC, Axin, β -catenin, α -catenin), NF κ B, Src and MITF. In parallel, pre and post-treatment tumor biopsy specimens will be processed for immunohistochemistry and stained for HSP client proteins implicated in therapeutic escape including BRAF, CRAF, AKT, phospho-AKT and phospho-ERK. All IHC work will be performed in [name] laboratory.

Additionally, biopsy specimens will be evaluated by Reverse Phase Protein Array (RPPA) at RPPA Core Facility, [name] Anderson Cancer Center (Texas, USA). Primary targets of interest for analysis of AT13387 effect on relevant HSP90 client proteins in tumor biopsy tissue will be evaluated. Frozen biopsy specimens obtained during collection will be sent for analysis of relevant proteins, protein post-translational modifications (phosphorylation and other modifications) and effects on relevant signaling pathways.

For FNA specimens, an 18-gauge needle should be used to perform multiple passes per needle, per sample under sterile conditions. For each pass, negative pressure was applied via the plunger on a 10 ml syringe to introduce adequate amounts of tissue into the needle bore. Following sampling, ~500 μ L of preservcyt was aspirated into the syringe and the contents of the syringe were expelled into a sterile 1.5 ml eppendorf tube. Samples were kept on dry ice for transport. Then the sample is centrifuged at 0.2 rcf to form a pellet, aspirated off the preservcyt using a 200 μ L pipet and a 200 μ L capillary/gel-loading

pipette tip. Aspirated preservcyt will be re-spun at 0.2 rcf, pelleting any remaining tissue/cells and remaining liquid was again aspirated off as waste. All samples are then placed at -20C for undergoing urea lysis the following day. For excisional specimens the same process will take place except 10-20 passes with a 18 gauge needle will be performed on the same in sterile conditions. Specimens will then be snap frozen in liquid nitrogen and stored in cryotubes before being transported to [name] lab at Moffitt.

It is not necessary to do FNAs if core needle biopsies or excisions can be performed instead. Furthermore, while liquid nitrogen is the preferred method of freezing specimens, using dry ice is allowable if it improves the chances of getting biopsies. Samples can also be transferred to [name] Lab at Massachusetts General Hospital for freezing and storing.

9.1.3 Blood BRAF test

Our group has developed a blood-based assay that can measure circulating BRAF levels in patients with BRAF mutant melanoma. (Panka *et al.*, 2010; Panka *et al.*, 2014) Our data shows that the BRAF level is reduced in patients treated with BRAF-directed therapy (both single-agent vemurafenib and the combination of DT) and, in some patients, increases in advanced of clinical or radiographic progression by 40-60 days. (Panka *et al.*, 2014) As this assay remains under clinical development, we plan to measure serial values (pre-treatment and at the beginning of each cycle) to further interrogate the utility of this assay. All samples will be initially processed in the Translational Research Laboratory at MGH and then subsequently assayed at the BIDMC.

9.2 Laboratory Correlative Studies

9.2.1 PK Analysis

9.2.1.1 Collection of Specimen(s)

Specimens will be collected as follows:

While the pharmacokinetic data of single-agent AT13387 and the combination of dabrafenib and trametinib are known, PK data of the triple combination will be done during this study. Clinically observed toxicities will be correlated with the possibility of delayed clearance of individual agents. Drug levels of AT13387, dabrafenib, and trametinib will be performed on day 1 of three-drug treatment (pre-, 1, 2, 4, 6, and 8 hours after dosing), day 2 (24 hours after day 1 dosing) as well as day 15 (pre-, 1, 2, 4, 6, and 8 hours after dosing), day 16 (24 hours after day 1 dosing). For the purpose of this study, post-treatment refers to post-infusions. All PK samples, inclusive of those drawn for oral agents, will be drawn at the same time relative to the end of infusion (+ 10 min).

Samples for trough level PK analysis will then be planned for each patient on day 1 of cycles 2, 4, 8, and 12.

Cycle(s)	Day of Collection	Planned Collection Time
1	1	Pre-treatment
	1	1.0 hr. post treatment
	1	2.0 hr. post treatment
	1	4.0 hr. post treatment
	1	6.0 hr. post treatment
	1	8.0 hr. post treatment
	2	24.0 hr. post treatment (C1D1)
	15	Pre-treatment
	15	1.0 hr. post treatment
	15	2.0 hr. post treatment
	15	4.0 hr. post treatment
	15	6.0 hr. post treatment
	15	8.0 hr. post treatment
	16	24.0 hr. post treatment (C1D15)
2, 4, 8, 12	1	Pre-treatment

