5. TREATMENT PLAN

5.1 Agent Administration

Treatment will be administered on an outpatient basis. A cycle of treatment will be 28 days in length. IV administration will begin approximately the same time oral agents are dosed, but not more than 10 minutes after oral agents are taken. For Cycle days 8 and 15, patients will be instructed to bring oral agents with them to be given in the clinic. Patients are asked to maintain a medication diary for recording each dose of Dabrafenib and Trametinib (Appendix D).

Reported adverse events and potential risks are described in Section 7. Appropriate dose modifications are described in Section 6. No investigational or commercial agents or therapies other than those described below may be administered with the intent to treat the patient's malignancy. The patient will be requested to maintain a medication diary of each dose of medication. The medication diary (Appendix D) and pill bottles will be returned to clinic staff at the end of each course. To document compliance, a pill count will be performed of all unused pills.

Dosing levels for the study are listed below in Table 5.1. Dose level 1 will be the first dose level. Intrapatient dose escalation will be allowed when safe and feasible once the next higher dose level has been cleared. Additional, intermediate dose levels may be enrolled under the following

conditions:

- 1) Toxicity is seen at a dose level where dose modification is necessary and the prior, lower dose level was treated without DLT or analysis of the PK data suggests that an intermediate dose would be appropriate;
- 2) An intermediate dose is conceivable based on the size of pills and nature of the toxicity at the higher dose;
- 3) Consensus agreement is made between investigators, industry sponsors, and CTEP;
- 4) CTEP and IRB approval of an amendment to the protocol that clearly describes the rationale for and the logistics of the intermediate dose level.

Table 5.1 Dose Escalation Levels for Phase I Study

Dose Level	Dabrafenib [BID/PO]	Trametinib [QD/PO]	AT13387 [D1,8,15/IV]
-1	75 mg	1 mg	180 mg/m ²
1	150 mg	1 mg	180 mg/m ²
2	150 mg	2 mg	180 mg/m ²
3	150 mg	2 mg	220 mg/m ²
4	150 mg	2 mg	260 mg/m ²

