5.1.3 AT13387

AT13387 is dosed in mg/m² using institutional standard of practice for dose calculations. AT13387 is administered via Infusion. Infuse over 1 hour through a central line or a well-defined peripheral vein (Note: an in-line filter is NOT required). If use a peripheral line, be sure to aspirate venous blood prior to starting the infusion. Check the

infusion site every 15 minutes and change the site of infusion should evidence of swelling or discoloration is observed. If AT13387 cannot be administered on Cycle Day 8 or 15, the dose will be skipped and not delayed.

If patient experiences pain along the infusion site, slow the infusion rate (i.e. > 1 hour duration) and/or infuse D5W through a “Y” connector. The additional volume of D5W dilutes AT13387 concentration at the local site of the infusion and alleviates the irritation.

In the event that trametinib, dabrafenib, or both agents need to be discontinued due to toxicity reasons, treatment with AT13387 may continue at the discretion of the investigator until time of disease progression.

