APPENDIX D DRUG DIARY

Study Participant Self-Administration Drug Diary

DFCI Study Number: 14-186

Participant Name: _____

Your Doctor _____ Phone _____

Your Nurse _____ Phone _____

Dosing Instructions for Dabrafenib:

Your dose of dabrafenib is _____ mg made up of _____ - _____ mg tablets. You take two doses of dabrafenib each day.

Dosing Instructions for Trametinib:

Your dose of trametinib is _____ mg made up of _____ - _____ mg tablets. You take one dose of trametinib each day.

- You will take trametinib once per day. You will take dabrafenib twice per day.
- You should take your first dose of dabrafenib and your dose of trametinib in the morning.
- You should not eat for two hours before taking dabrafenib and trametinib.
- You should not eat for one hour after taking dabrafenib and trametinib.
- Approximately 12 hours after your morning dose of dabrafenib, you should take an evening dose of dabrafenib. You again should not eat two hours before and one hour after taking dabrafenib.
- Dabrafenib should be stored at room temperature. Trametinib should be refrigerated.
- Vomited doses should not be made up. Missed doses of trametinib should not be made up if more than 6 hours have lapsed from the scheduled/planned dose time (i.e. no more than 30 hours from the previous dose). Missed doses of dabrafenib should not be made up if it is less than 6 hours until the next scheduled dose.
- Please contact your study staff immediately if you develop a fever, which is defined as a temperature of 38.5° Celsius or 101.3° Fahrenheit
- Each of the study drugs must be kept in the original container they are distributed in
- Please remember to bring back any unused study drug, all empty containers, and your diary to the next clinic visit
- Wash your hands with soap and water after taking your dose

DOSING LOG: Cycle ____ Date of Day 1: _____

Dosing Log Instructions

- Make sure to indicate the date, time, amount taken and any comments immediately following each dose.
- Bring your study drug containing all remaining medication, including empty bottles, to each visit.
- Once complete, provide this signed or initialed and dated dosing log to your study doctor or nurse.

Day	Date	Time of Dose	Dabrafenib Dose (mg)	Time of Dose	Dabrafenib Dose (mg)	Time of Dose	Trametinib Dose (mg)	Comments If dose was vomited, missed or skipped, indicate reason below.
1		am		pm		am		
2		am		pm		am		
3		am		pm		am		
4		am		pm		am		
5		am		pm		am		
6		am		pm		am		
7		am		pm		am		

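### All post-dose PK draws are timed from the end of the AT13387 infusion, about an hour or more after the oral doses, and Day 1 oral-agent summaries can pool first-dose with already-treated patients (minor)

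*Combined protocol and SAP*

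**What the plan says.** **Clock.** Section 9.2.1.1 schedules draws pre-treatment and at 1, 2, 4, 6, 8 and 24 h. It defines the reference point as "For the purpose of this study, post-treatment refers to post-infusions" and adds "All PK samples, inclusive of those drawn for oral agents, will be drawn at the same time relative to the end of infusion", with a 10 min window. Section 5.1 says "IV administration will begin approximately the same time oral agents are dosed, but not more than 10 minutes after oral agents are taken". Section 5.1.3 says "Infuse over 1 hour through a central line or a well-defined peripheral vein" and allows a slower infusion if there is pain.

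**Other descriptions of the schedule.** Section 2.4.1 and footnote k of the Study Calendar (Section 10) count hours from the dose. Section 2.4.1 describes a full profile on Cycle 1 Day 15 only, while 9.2.1.1 and footnote k have Days 1 and 15. The text of 9.2.1.1 has a draw on "day 16 (24 hours after day 1 dosing", whereas its own table refers that draw to Day 15. Section 9.2.1.2 keeps the oral-agent samples when AT13387 is not given.

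**Order of draw and oral dose.** Section 5.1 says "For Cycle days 8 and 15, patients will be instructed to bring oral agents with them to be given in the clinic". The diary (Appendix D) says "You should take your first dose of dabrafenib and your dose of trametinib in the morning". Neither addresses the 24 h draw on Days 2 and 16.

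**Population and analysis.** Section 3.1.1 admits patients with or without prior BRAF-targeted therapy, and 3.2.1 lets patients enter on dabrafenib and trametinib without wash-out. Section 13.3 plans descriptive statistics for Cmax, AUC and Tmax. It explores prior therapy only against efficacy outcomes, and it names no AUC rule.

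**The concern.** The sampling clock belongs to one drug but serves three. Drugs swallowed before the infusion starts are first sampled about two hours later, and AT13387 is first sampled an hour after its infusion stops. A value labelled 1 h therefore means different things for different drugs, and the text is not consistent about which clock applies.

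The Day 1 question is separate. A first-dose trametinib profile and a profile from a patient at steady state are different quantities. One mean or coefficient of variation over both describes neither.

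What is at stake is the accuracy and comparability of descriptive PK. That is a named secondary objective (1.1.2.2), it is reviewed before cohort expansion (schema text), and it is one route to an added dose level where "analysis of the PK data suggests that an intermediate dose would be appropriate" (5.1).

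**Working it through.** The plan gives no figure of its own for these quantities, so there is none to reproduce.

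**1. Draw times on the oral clock.** Time after oral intake = lag (0-10 min) + infusion (60 min) + nominal time + window (0-10 min).

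| Nominal (h) | Earliest (h) | Latest (h) |
|---|---|---|
| 1 | 2.00 | 2.33 |
| 2 | 3.00 | 3.33 |
| 4 | 5.00 | 5.33 |
| 6 | 7.00 | 7.33 |
| 8 | 9.00 | 9.33 |
| 24 | 25.00 | 25.33 |

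If the window is meant as plus or minus, the first draw is at 60 + 60 - 10 = 110 min (1.83 h) at the earliest. A slowed infusion makes every draw later. Pre-treatment and trough samples are unaffected.

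**2. Tmax.** Single-dose medians are 1.5 h for trametinib (2.2.1.2) and about 2.0 h for dabrafenib (2.2.2.2). No draw lies between pre-dose and about 2 h, so no oral Tmax in that interval can be recorded.

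**3. AT13387 Cmax.** The half-life is 6.6 to 11.5 h (2.2.3.3). Assume the peak is at the end of infusion, followed by mono-exponential decline. Loss = 1 - 2^(-t/h).
- t = 60 min: 1 - 2^(-1/11.5) = 5.8%; 1 - 2^(-1/6.6) = 10.0%.
- t = 70 min: 6.8% and 11.5%.

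**4. Oral Cmax.** Trametinib on Day 15, with a peak:trough ratio of about 2 (2.2.1.2), halves over 24 - 1.5 = 22.5 h. A first draw 0.5 to 0.83 h past the peak loses 1 - 2^(-0.5/22.5) = 1.5% to 1 - 2^(-0.83/22.5) = 2.5%. For dabrafenib (one compartment, half-life 8 h, Tmax 2.0 h), C(2.33 h)/Cmax = 0.994, a loss under 1%. Section 2.2.1.2 gives between-subject variability in trametinib Cmax of 27-50%.

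**5. Early oral AUC (illustration).** This uses a one-compartment single-dose model, linear trapezoids and an assumed Tmax of 1 to 3 h. Estimated AUC over 0-9 h is 88-95% of true for dabrafenib and 90-94% for trametinib. The same nominal times counted from the dose give 95-98% over 0-8 h.

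**6. Day 1 pooling, trametinib.** The accumulation ratio is 6.6 (2.2.1.2). Set first-dose AUC to 1 and assume superposition and dose proportionality. A patient at steady state on the study dose has 5.6 + 1 = 6.6. A patient at steady state on 2 mg who moves to 1 mg has 5.6 x 2 + 1 = 12.2.
- One of 3, arithmetic mean: (6.6 + 1 + 1)/3 = 2.87; (12.2 + 1 + 1)/3 = 4.73.
- One of 3, geometric mean: 6.6^(1/3) = 1.88; 12.2^(1/3) = 2.30. The median stays a first-dose value.
- One of 6, arithmetic mean: (6.6 + 5)/6 = 1.93; (12.2 + 5)/6 = 2.87.
- Two of 3: the median is itself a carried-over value.

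By Day 15 a first-dose patient is near steady state: with an effective half-life of 4.5 days, 1 - 2^(-15/4.5) = 90%. Pooling is therefore mainly a Day 1 matter. AT13387 is unaffected, because prior HSP90 inhibitor therapy is excluded (3.2.2).

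**The case against.** The strongest reply is that one shared clock for three drugs is an openly stated trade-off and the losses are small. That stands. PK here is descriptive, no decision threshold turns on a shift of this size, and an intermediate dose level also needs consensus and an approved amendment (5.1).

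A reader might infer that a 4 h or 6 h draw should be moved to the end of infusion. The documents do not support that as a correction. Sections 2.4.1 and 9.2.1.1 aim to relate toxicity to delayed clearance, which needs declining-phase points. The dabrafenib 24 h draw follows the evening dose, so the morning dose leaves points at about 3, 5, 7 and 9 h. Dropping the 5 h or 7 h point raises the slope standard error by sqrt(20/18.67) = 1.035 and cuts per-patient residual degrees of freedom from 2 to 1. For AT13387 AUC to the 24 h draw (one compartment), the move changes the error from -6.0/-4.0% to about zero with linear-up/log-down trapezoids. With linear trapezoids it changes it from +2.3/-0.3% to +8.4/+3.8% (half-lives 6.6/11.5 h). Whether it helps depends on a rule that 13.3 does not name.

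It is also fair to say that some conflicts are editorial. The table in 9.2.1.1 corrects the Day 16 reference, and the definition there favours the infusion clock. Actual dose and draw times are recorded (9.2.1.2), and the PK laboratory manuals, not available here, may settle more. What remains is the contradiction over profile days, the missing anchor when AT13387 is skipped, and a calendar footnote that would lead a site to draw about an hour earlier. Recorded times cannot supply a sample that was never drawn.

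On pooling, the reply is that it needs a retained Day 1 profile, patients who enter on both drugs, and an unsplit summary. That is right, and it is why the claim is only that summaries can mix. Section 13.3 neither plans nor rules out a split.

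**Conclusion.** The point holds as a minor one. On the stated definition, every post-dose oral-agent draw is at least an hour later on the oral clock than its label (nominal times, 1 h infusion). Trametinib Tmax near 1.5 h is unobservable. AT13387 Cmax is low by about 6-10%, given a peak at the end of infusion and the quoted half-lives. Oral Cmax is barely affected.

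The Day 1 factors of 2.9 and 4.7 rest on the accumulation ratio of 6.6, dose proportionality, one patient assumed to be at steady state in a cohort of three and, for 4.7, a 1 mg study dose after 2 mg. How many patients will enter on these drugs is not given and may be none, although 2.3 notes that wash-out requirements make such patients hard to enrol.

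Two stronger readings are not supported. One is that the MTD determination is compromised: it rests on Cycle 1 DLT counts (5.2, 13.1), not on PK. The other is that Day 1 PK will be uninterpretable: that depends on an unknown patient mix, and the Day 15 profile is largely unaffected.

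**What to change.** 1. In 13.3, summarise Day 1 dabrafenib and trametinib PK separately by whether the patient was on these drugs at entry, using the Day 1 pre-treatment sample to confirm carry-over. The cost is smaller groups in each summary.
2. In 13.3, compute parameters from the recorded actual times, counted from oral intake for dabrafenib and trametinib and from the infusion for AT13387. Name the AUC rule. State that oral Tmax below about 2 h cannot be observed and that the earliest post-infusion AT13387 value, reported as Cmax, is taken 1 h after the infusion ends.
3. Reconcile 2.4.1, 9.2.1.1, 9.2.1.2 and footnote k, checking against the PK laboratory manuals, on: the profile days; the clock; the reference dose for the Day 16 draw; the anchor when AT13387 is skipped; and whether the Day 2 and Day 16 draws come before that morning's oral doses.

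All three are text changes with no extra blood draws. Replacing the 4 h or 6 h draw with one at the end of infusion is optional. If it is considered, decide it together with the AUC rule, because it gives up a declining-phase point.

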9.2.1.2 Handling of Specimens(s)

For each sample, the date and time of the dose and the date and time of the PK sample draw will be recorded and keep as Source Documentation in each individual patients chart.

Details for AT13387 PK collection and process are provided in the “AT13387 Pharmacokinetic Laboratory Manual.”. Note: This manual will be disseminated with the clinical protocol and is also available to investigators on request from the coordinating center.

AT13387 PK Samples

If AT13387 was not administered at Cycle day 8 or 15, PK samples will only be drawn for dabrafenib/trametinib for that time point.

1. At each time point, collect 4 mL whole blood PK sample into a properly labeled 4 mL Lithium Heparin blood collection tube. Record the date and time each sample is collected. **Note the sampling time and volume of blood collection may differ with specific protocols and/or regimens.**
2. Immediately after collection, gently invert (do not shake) the evacuated blood collection tube for 30 seconds, then place on a standard roller for a minimum of 5 minutes. If a blood roller is not available, continue to invert the tube a further 8 – 10 times. Blood samples should be processed into plasma within 1 hour of sample collection
3. Centrifuge the tube at 1100 - 1500g for 10-15 minutes at 4-8° C within 1 hour of

sample collection.

4. Immediately transfer plasma into two 2.0 mL Matrix TrackMate ScrewTop tubes, each containing approximately 0.75 mL of plasma.
5. Store at -20°C until shipped.
6. Ship all frozen plasma samples on dry ice

Details for dabrafenib and trametinib PK collection and process are provided in the “Pharmacokinetic Laboratory Manual”. Note: This manual will be disseminated with the clinical protocol and is also available to investigators on request from the coordinating center.Dabrafenib/Trametinib PK Samples

Due to the potential instability of trametinib, pharmacokinetic blood samples collected for the determination of trametinib/dabrafenib concentration in plasma will be collected in 2 mL K2-EDTA blood tubes.

1. At each time point, collect 2 mL whole blood PK sample into a properly labeled 2mL K2EDTA evacuated blood collection tube. Record the date and time the sample is collected. **(Note the sampling time and volume of blood collection may differ with specific protocols and/or regimens.)**
2. Immediately after collection, gently invert (DO NOT SHAKE) the evacuated blood collection tube 8-10 times to mix the K2EDTA anticoagulant with the whole blood. Blood samples MUST be placed on wet ice immediately after mixing the blood with the anticoagulant. Blood samples should be processed into plasma within 15 minutes of collection (30 minutes maximum).
3. Centrifuge the sample at 2500 to 3000 rpm for 10 to 15 minutes in refrigerated centrifuge to achieve a clear plasma layer over the red cells. The speed and time may be varied according to the make and model of centrifuge used.
4. Immediately transfer plasma into a corresponding pre-labeled 1.8 mL NUNC tubes (each containing approximately 0.75 mL of plasma).
5. Store at -20 °C until shipped.
6. Ship all frozen plasma samples on dry ice, overnight.

